## 1. Abstract

It is estimated that nearly 25.8 million people in the United States have type 2 diabetes mellitus. Research over the last decade has shown that obstructive sleep apnea (OSA) is a common condition in people with diabetes. Data from a number of different studies show that the prevalence of moderate to severe OSA in diabetics is approximately 50%. Observational and experimental evidence also indicates that intermittent hypoxemia and recurrent arousals in OSA may alter glucose metabolism and worsen glycemic control. However, the impact of treating OSA with positive airway pressure (PAP) therapy on glycemic control is not well defined. Adequately powered randomized clinical trials have yet to be performed to demonstrate whether PAP therapy for OSA in diabetics can improve glycemic control, decrease blood pressure, and reverse endothelial dysfunction. The overarching goal of this study is to determine whether PAP therapy for OSA in diabetics with less than optimal glycemic control leads to improvements in (a) glycosylated hemoglobin (HbA1c); (b) glycemic variability as assessed by self-monitoring of blood glucose and continuous monitoring of glucose; (c) blood pressure; and (d) endothelial function. We propose to conduct a randomized control trial in people with diabetes and moderate to severe OSA who will be randomly assigned for 3 months to PAP therapy along with healthy lifestyle and sleep education (PAP-HLSE) or healthy lifestyle and sleep education (HSLE alone).

## 2. Objectives (include all primary and secondary objectives)

Primary Objectives: To examine whether treatment of OSA with PAP in diabetics has favorable effects on glycemic control, postprandial hyperglycemia, and glycemic variability.

Secondary Objectives: To assess whether treatment of OSA with PAP in diabetics improves 24-hr blood pressure and endothelial function.

## 3. Background

Obstructive sleep apnea (OSA) is a chronic condition characterized by repetitive collapse of the upper airway during sleep. The resulting decrease in airflow leads to episodes of intermittent hypoxemia and recurrent arousals that, in turn, trigger a repertoire of physiological events including: (a) activation of the sympathetic nervous system, (b) increase in oxidative stress, (c) alterations in corticotropin function, and (d) release of inflammatory adipocytokines. Collectively, these alterations likely form a synergistic and interactive network that has a negative impact on normal glucose homeostasis. Thus, it is not surprising that an independent association has been demonstrated between OSA, insulin resistance, glucose tolerance, and diabetes.

The prevalence of OSA in diabetes has been a topic of significant research and data published to date show that at least 50% of diabetics have OSA. In the community-based Sleep Heart Health Study, 58% of middleaged and older adults with diabetes were reported to have OSA. Recent findings from Sleep AHEAD study, an ancillary to the Look AHEAD trial, corroborate the high prevalence of OSA in diabetes. Approximately, 53% of the diabetics in the Sleep AHEAD study had moderate to severe OSA (AHI  $\geq$  15 events/h). Given the abundance of data linking OSA to abnormalities in glucose metabolism, a much sought after quest has been to assess the impact of OSA on glycemic control in diabetes and determine whether OSA treatment with continuous positive airway pressure (PAP) therapy can improve hyperglycemia.

[figure not shown]
Despite the potential relevance of OSA in glycemic control and diabetes-related comorbidity, only a handful of studies have evaluated whether PAP treatment for OSA in type 2 diabetes is associated with improvements in metabolic function. Of these, only two are randomized clinical trials, with the rest being uncontrolled pre-post assessments after the initiation of PAP therapy. The first randomized clinical trial showed no change in HbA1c in diabetics with PAP therapy. The lack of positive effect in that study could be attributed to several methodological issues including the small study sample (20 PAP treated; 22 controls), the limited duration of follow-up (3 months) and the suboptimal adherence to PAP (3.6 hours/night). Similarly, the second randomized clinical trial also showed that in diabetics PAP therapy for OSA for 3 months has no effect on glycemic control. The lack of a favorable effect of PAP on metabolic control was mostly likely related to the fact that two-thirds of the sample already had good metabolic control at baseline with an HbA1c within the target therapeutic range

(HbA1c < 7.5%). It should come as no surprise that there is a “floor effect” beyond which HbA1c cannot be improved despite optimal treatment of OSA.

Given the paucity of controlled studies, our overarching objective is to conduct a sufficiently robust randomized clinical trial to determine whether PAP treatment of moderate to severe OSA in diabetics with less than optimal glycemic control is associated with improvements in glycemic control, postprandial hyperglycemia, and glycemic variability.

#### 4. Study Procedures

**Study Design:** Randomized Clinical Trial (PAP therapy + Healthy Lifestyle and Sleep Education [HLSE] versus Healthy Lifestyle and Sleep Education Only). The figure on the following page describes the schema for the study protocol (Note: The diagram does not show every study related procedure).

#### Study protocol outline:

1. Assess eligibility (via phone) of volunteer participants responding to ads, flyers, or mailings for the study protocol (see inclusion and exclusion criteria below). Based on whether the participant meets the additional criteria, a visit will be scheduled with the study team for informed consent.
2. If a participant does not have any exclusion criteria based on our preliminary screen, a home self-applied monitor (ApneaLink®) will be provided to the participant to record for one night of sleep. These monitors allow for a limited assessment of breathing abnormalities during sleep because only a few channels for physiologic recordings (e.g., oxygen saturation, respiratory effort) are recorded. Analysis of the acquired physiological signals will be used to calculate the oxygen desaturation index (ODI = number of oxygen desaturation per hour of sleep). Only those volunteer participants with an ODI  $\geq 15$  events/hr (i.e., at least moderate OSA) will be considered for further screening. A blood sample (10 ml) for hemoglobin A1c (HbA1c) will also be obtained to exclude those that have good glycemic control (HbA1c < 6.5%).
3. Diabetics with previously untreated OSA will be required to demonstrate that they tolerate wearing the PAP device during sleep. Each participant will be given a PAP device which they can keep for a minimum of 3 nights. The PAP device will need to be used at least 4 hours/night on at least three nights for continued participation. After the PAP Run-In period use and until the extended montage sleep study, the participant will also wear an activity meter (Actigraph) which will allow us to characterize habitual sleep patterns. Because habitual short sleep duration and poor sleep hygiene are known to alter glucose metabolism, we will exclude participants with poor sleep hygiene which will be defined as erratic or inconsistent sleep habits or average sleep duration of < 6 hours.
4. If a participant shows that he/she is able to use the PAP device for the minimal required duration, a

extended-montage sleep study (which includes EEG, EMG, etc.) will be then conducted to characterize sleep quality and breathing abnormalities. If the sleep study shows that the participant does not have moderate to severe OSA, they will not be able to proceed further. We suspect that the number of participants with a positive home sleep test but a negative full-montage sleep study will be minimal. The most likely cause of a positive home sleep test and a negative full-montage study are differences in alcohol use or weight between the two tests. Alcohol can increase the collapsibility of the upper airway during sleep. Thus, if a participant were to drink on one night but not the other study, it is possible to get different ODI values. Moreover, if a modest amount of time passes between the two sleep tests, weight loss is possible, but unlikely. Differences in weight can also result in different ODI values. Thus, to minimize differences in conditions between the two tests, we will request that all participants refrain from any alcohol the night of the evaluations. Furthermore, we will minimize the time window between the two tests to avoid any significant alterations in health habits that could lead to a change in weight.

5. If all of the inclusion/exclusion criteria are satisfied (e.g., OSA defined as an apnea-hypopnea index of at least 15 events/hr with overnight polysomnography and the ability to tolerate PAP), the participant can continue on into the study.

#### **Procedures to be conducted to assess eligibility:**

1. **Home Sleep Testing:** The sleep monitor with a limited montage (ApneaLink®) device is a simple self-applied screening tool for OSA. The ApneaLink® device is capable of monitoring several physiologic signals (i.e. oximetry, nasal cannula) during sleep. These devices are battery powered and provide information on the number of oxygen desaturation episodes during sleep.
2. **Wrist actigraphy:** Measurements of activity are commonly used as surrogate markers to infer the duration of average sleep. Actigraphs are simple portable accelerometers that monitor motion/activity data. These units are built as wrist-size watches and are typically worn on the wrist. Eligible participants that agree to participate in the proposed research will be given an actigraph to monitor usual sleep habits. The watch provided can be worn throughout the PAP Run-In period and, if the subject is eligible for the trial, he/she can continue wearing the same watch until the morning of randomization.
3. **Blood Tests:** Measurements of HbA1c will be performed to get a current value.
4. **Extended montage sleep study:** Standard methods for conducting a screening sleep study will be employed. The full montage sleep recording can be performed in the participant's home or in a sleep laboratory environment using similar equipment. These recordings include continuous monitoring of left and right electro-oculograms, surface electroencephalograms, submental and anterior tibialis electromyogram, oronasal airflow, pulse oximetry, thoracic and abdominal movements with piezoelectric gauges, and a modified electrocardiographic lead.

#### **Procedures to be conducted as part of the clinical trial:**

1. **Questionnaires:** Basic demographic factors (race, marital status, education, work status, smoking history, alcohol history, and caffeine consumption), sleep-related symptoms, and prevalent medical conditions will be assessed with the Medical History and Sleep Survey. Quality of life will be ascertained using the Medical Outcomes Short-Form 36 (SF-36), Functional Outcomes of Sleep Questionnaire (FOSQ), and the Sleep Apnea Quality of Life Index (SAQLI). To determine a participant's habitual activity level, the Minnesota Leisure Time Physical Activity Questionnaire (PAQ) will be used. Time points for data collection: Before randomization and 3 months.
2. **Anthropometry:** Standard methods will be employed for measurements of weight, height and for neck, waist, and hip circumferences. For example, measurement of neck circumference will be performed by using an inelastic tape that is applied around the neck just below the laryngeal prominence. Waist circumference will be measured at the narrowest part of the torso, at the end of normal expiration. For

obese participants, the smallest horizontal circumference between the ribs and the iliac crest will be measured. Hip circumference will be measured around the buttocks in a horizontal plane at the level of the maximal extension of the buttocks. Time points for data collection: Before randomization and 3 months

3. **Clinic Blood Pressure:** Resting arm blood pressure will be obtained in triplicate using a conventional mercury sphygmomanometer. Cuff size will be determined by measuring the circumference of the upper arm, measured at the midpoint, and identifying the appropriate bladder size from a standard chart. Measurements will be repeated three times and recorded. Time points for data collection: Time points for data collection: Before randomization, 2 weeks, 1 month, 2 months, and 3 months.
4. **24 Hour Blood Pressure:** Participants will be instructed in the use of a 24 hour ambulatory blood pressure monitor. The device consists of a blood pressure cuff that is connected by rubber tubing to a small pressure monitoring device that weighs only 9 oz and fits easily in a shirt pocket. The device will be programmed to measure blood pressure at hourly intervals for the subsequent 24 hours. Time points for data collection: Before randomization and 3 months
5. **Blood Draw:** Venous blood will be collected in vacutainer tubes. Approximately 50 ml of venous blood will be drawn and equally distributed across 6-7 vacutainer tubes with approximately 7 ml in each tube. Serum/plasma will be extracted from venous blood, stored, and assay for the analytes of interest in batches for efficiency. Time points for data collection: Before randomization, 2 weeks, 1 month, 2 months, and 3 months.
6. **Self-Monitoring of Blood Glucose (SMBG):** Each participant will be instructed to record a 7-point SMBG profile (fasting, preprandial/2-hr postprandial at each meal, bedtime) on 3 consecutive days. A commercially available glucometer will be provided by the study along with the glucose measuring strips. The values from the 7-point SMBG will be recorded by the study participant on a paper diary. SMBG profiles are commonly used in the clinical practice for improving glycemic control in diabetics. Time points for data collection: Before randomization and 3 months.
7. **Continuous Glucose Monitoring (CGM):** A continuous glucose monitoring recorder will be used for assessing the 24-hour interstitial glucose profiles. A sterile disposable glucose sensor (Dexcom) will be placed on the skin of the abdomen and another on the area of the triceps (Abbott). Data on interstitial glucose values are automatically transmitted to a wireless monitor every 5 minutes. The CGM system provides continuous measurement of glucose concentration in interstitial fluids over a range of 40 to 400 mg/dL. The CGM recorder will be used for 2 weeks. In clinical practice, CGM is commonly used to assess the effects of meals, exercise, and medication on a patient's glucose levels. Time points for data collection: Before randomization and 3 months.
8. **Endothelial Function Using Peripheral Arterial Tonometry (PAT):** PAT will be measured using the Endo-PAT device (Itamar Medical). This test requires approximately 20 minutes and is performed with participants positioned supine in a quiet environment with dimmed lighting. The participant is asked to remove rings and whether they have allergies to latex. Fingernails are trimmed if overly long. Probes (one-time use only) are then placed on the index finger of each hand. A blood pressure cuff is placed on the non-dominant arm. Following a brief period (5 minutes) of baseline recordings, the cuff is inflated to 60 mmHg above their systolic blood pressure determined earlier (to at least 200 mmHg but not more than 300 mmHg) to occlude blood flow in the arm. The period of occlusion is timed with a stop watch for 5 minutes. At exactly 5 minutes, the pressure is rapidly released and readings taken for a minimum of 5 minutes. Once recording is complete, the probes are removed and discarded. Time points for data collection: Before randomization and 3 months.
9. **Assessment of Body Fat:** Total body fat, a major confounder in the relationship between sleep disturbance and glycemic control, will be obtained using Dual-Energy X-Ray Absorptiometry (DEXA) scan. The

DEXA scan is used to measure body composition in terms of fat and fat-free mass. DEXA systems are used to perform whole-body scans in order to determine the bone and soft tissue composition of the whole body and subregions such as arms, legs, and trunk. The body is partitioned into three segments: bone, fat, and fat-free mass. A total body scan takes 6 minutes and the radiation dose incurred during DEXA scanning is approximately 0.5 millirem, which is a very small dose. DEXA is a simple and safe technique that is routinely performed in clinical care and imposes minimal participant burden. Time points for data collection: Before randomization and 3 months.

**10. Food Diary:** All participants will be required to document their dietary intake for 3 days during the acquisition of the 7-point SMBG and CGM data. Time points for data collection: Before randomization and 3 months.

**11. Home sleep monitoring:** At the 3 month visit, home sleep testing will be repeated (ApneaLink®) and also the actigraph as done during the screening phase.

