**Procedures to be conducted as part of the interventions:**

After completing the required testing, participants will be randomly assigned to one of two treatment groups: Healthy Lifestyle and Sleep Education alone (HLSE) or HLSE plus PAP (HLSE-PAP).

- 1. HLSE intervention:** Lifestyle guidelines developed by the American Heart Association and American Diabetes Association for disease prevention and weight loss will be provided to all subjects. Compliance with anti-diabetic medications will be emphasized. In addition, counseling on sleep hygiene using published materials to suggest ways to improve the regularity and duration of sleep, aiming for 7-8 hours of sleep per night. General lifestyle advice relevant for OSA will also be provided, including a recommendation for regular exercise and avoidance of alcohol, particularly near bedtime.
- 2. PAP therapy:** This intervention includes OSA treatment with PAP, titrated using a home-based computerized auto-titration protocol. Participants will have an opportunity to try various PAP mask interfaces in order to optimize fit. Verbal and written directions on the use of these materials will be provided, with instructions reinforced after the initial period of PAP titration is completed, and then at scheduled telephone follow-up calls. After each night of use, the recorded data on usage are transmitted from the participant's home to a central computer using a wireless communication feature in the PAP device. The research team will review the transmitted data and judge its acceptability based on usage for at least 4 hours/night for at least 3 nights during the run-in period. After randomization, PAP data will be visually reviewed to identify the optimal pressure, defined as the pressure that eliminates 90% of airflow limited events.

We recognize that some participants will have less than optimal PAP adherence after enrollment. In participants that use PAP more than 5 h/night during the study, we will provide positive reinforcement regarding their PAP use. In those participants where the use of PAP is poor, we will use Motivational Enhancement Therapy (MET), which is based on the principles of motivational interviewing. Each participant having difficulty with PAP therapy will be asked to provide a subjective assessment of wearing PAP; expected barriers and facilitators of use; and motivation and confidence to use PAP. Issues that are raised will be addressed to improve adherence to PAP.

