### b. Secondary outcome variables.

- BP, Endothelial Function
  - 24-hr BP profile
  - Endothelial function (Endo-PAT)
- Sleepiness and Quality of Life Assessments
  - Subjective sleepiness (Epworth Sleepiness Scale)
  - Quality of Life (SF-36, SAQLI, FOSQ)

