The secondary outcomes include change in: (1) CGM-derived mean glucose values; (2) systolic, diastolic and mean daytime and nighttime BP; (3) heart rate variability derived indices of sympathovagal balance; (4) endothelial function (Endo-PAT derived reactive hyperemia index); (5) markers of oxidative stress (e.g., oxidized LDL); (6) lipid abnormalities (e.g., LDL, HDL, triglycerides); (7) myocardial injury (troponin-I); and (8) renal injury (urinary albumin and creatinine). All analyses for our secondary outcomes will be done under the intention to treat principle. Initial analyses will tabulate baseline characteristics of participants by randomization group. For our continuous outcomes, we will use multivariable regression and mixed model repeated measures analyses as done for the primary outcomes.

Sample Size Determination:

Sample size was calculated based on the magnitude of anticipated improvement in our primary outcome (e.g., standard deviation [SD] of Dexcom CGM glucose values). The primary assumption for determining sample size was an expected mean decrease in SD of CGM glucose values of 3.3 mg/dl (SD: 6.9 mg/dl) with PAP therapy with no expected change in the control group. Assuming a type 1 error and a power of 90%, a sample size of 92 participants would be needed in each arm (total N=184). To account for modest dropout (~10%), the enrollment goal was 102 participants in PAP therapy arm and 102 participants in the control arm. A total sample size of 184 participants would also allow the study to detect a mean HbA1c difference of 0.36% between the two groups. Enrollment began in December 2014 and ended in December 2019 with a final sample size of 186 participants. In response to the COVID19 pandemic, all clinical research activities ended in early March 2020.

d. Early stopping rules.

Not applicable.

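### Hourly ambulatory BP readings leave some avoidable noise in daytime and 24-hour BP change, a modest loss of precision in a secondary outcome

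*Combined protocol and SAP*

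**What the plan says.** Section 4, item 4 of the trial procedures (24 Hour Blood Pressure), sets one rate for the whole recording: "The device will be programmed to measure blood pressure at hourly intervals for the subsequent 24 hours". Recordings are made before randomization and at 3 months.

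The recording serves a named objective. Section 2 lists as secondary "To assess whether treatment of OSA with PAP in diabetics improves 24-hr blood pressure and endothelial function", section 7b lists "24-hr BP profile", and section 7c analyses change in "systolic, diastolic and mean daytime and nighttime BP".

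Two statements bear on how the 24 hours divide. The education intervention counsels sleep hygiene, "aiming for 7-8 hours of sleep per night", and screening excludes people with "average sleep duration of < 6 hours".

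The documents give no reason for the hourly interval. They set no repeat recording, minimum number of valid readings, rule for failed readings or definition of day and night, and they give no precision or sample-size calculation for BP.

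**The concern.** A period mean built from few readings has sampling error of its own, and that error enters the change score twice, once at each visit. It adds to the variance of BP change and so widens the confidence interval for the treatment effect. A BP result near zero is then a little harder to interpret.

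More cuff inflations at night could disturb sleep, and the baseline recording starts at the extended-montage sleep study (section 4, study duration and visits). That is a reason for restraint at night. It does not apply to waking hours, where the recorder could be set to a shorter interval at little cost.

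**Working it through.** **The plan's own figure.** There is none for BP. The only full calculation (section 7c) is for the SD of CGM glucose: a difference of 3.3 and an SD of 6.9 mg/dl at 90% power. With two-sided alpha 0.05 (assumed, since no value is printed), 2 × (1.960 + 1.282)² × 6.9² / 3.3² = 91.9. This reproduces the stated 92 per arm and does not depend on BP.

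**Readings per recording.** Hourly for 24 hours gives 24 scheduled readings. With 8 hours of sleep, 16 are waking; at the 6-hour eligibility limit, 18 are. Failed readings lower both counts.

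**Assumptions (not in the documents).** Single-reading SD within a period s = 10 to 12 mmHg. SD of the observed 3-month change C = 8 to 12 mmHg, also used for the 24-hour mean. 8 hours of sleep.

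**Daytime mean, independent readings.** With k readings at each visit, reading noise contributes 2s²/k to the variance of change.

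| | s = 10, C = 12 | s = 12, C = 8 |
|---|---|---|
| Hourly, k = 16 | 12.5 of 144 (9%) | 18 of 64 (28%) |
| Cut with 30 min, k = 32 | 6.25/144 = 4.3% | 9/64 = 14.1% |
| Cut with 20 min, k = 48 | 8.33/144 = 5.8% | 12/64 = 18.8% |

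Starting from 18 waking readings, the 30-minute cut is 3.9% and 12.5%.

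On the BP scale, the unadjusted difference detectable with 92 per arm at 90% power is 3.242 × SD × √(2/92) = 0.478 × SD. With 30-minute readings it falls from 5.7 to 5.6 mmHg (change SD 12 to 11.74) or from 3.8 to 3.5 mmHg (change SD 8 to 7.42).

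**24-hour mean, only waking readings made denser.** Hourly noise is 2s²/24. With the day denser and the night at 8 readings, the time-weighted noise is 2[(2/3)²s²/k + (1/3)²s²/8].
- s = 10, C = 12: 8.33 falls to 5.56 (30 min) or 4.63 (20 min), a cut of 1.9% or 2.6% of 144.
- s = 12, C = 8: 12 falls to 8.0 or 6.67, a cut of 6.3% or 8.3% of 64.

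**Nighttime mean.** The night stays hourly, so its precision does not change.

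**Daytime mean, autocorrelated readings.** Let a share w of s² be independent noise and let the rest have correlation ρ^h at a lag of h hours. The error of interest is the sampled mean minus the true mean over 16 waking hours. For the correlated part, with readings at interval midpoints, the mean squared error per unit variance is:
- ρ = 0.3: 0.0122 hourly and 0.0031 at 30 min.
- ρ = 0.5: 0.0072 hourly and 0.0018 at 30 min.

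The independent part has 1/16 = 0.0625 and 1/32 = 0.03125. The 30-minute cut is 2s²[w × 0.03125 + (1 − w) × (drop in the correlated part)]/C².
- Lowest (w = 0, ρ = 0.5, s = 10, C = 12): 200 × 0.0054/144 = 0.7%.
- Highest (w = 0.5, ρ = 0.3, s = 12, C = 8): 288 × (0.0156 + 0.0046)/64 = 9.1%.

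So the range is about 1 to 9%.

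**Reading-level model.** This check shows what such a model would need. Suppose all readings are analysed with a participant intercept only and 16 daytime readings per visit. True change variance is T = C² − 2s²/16. It leaks into the residual, which becomes s² + 32(T/4)/31.
- s = 10, C = 12: T = 131.5, residual 133.9, model variance of change 2 × 133.9/16 = 16.7 against a true 144. The standard error is √(16.7/144) = 0.34 of its correct value.
- s = 12, C = 8: T = 46, residual 155.9, 19.5 against 64, ratio 0.55.

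A participant-by-visit effect is therefore required in any such model.

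**The case against.** The strongest case against is that the benefit is small and rests on assumptions. For the 24-hour mean, the quantity named in the objective, the best case is 2 to 8% of variance, or about 1 to 4% of the SD. The top of the daytime range pairs the noisiest readings with the smallest change SD, and positive autocorrelation shrinks the gain further. Sampling rate against cuff burden is a design preference, and the documents contain no contradiction here. Data collection is also over: section 7c records that enrollment ended in December 2019 and research activities in early March 2020. All of this stands. It limits the point to a minor improvement.

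A reader might infer that nighttime BP is the worse problem because it rests on fewer readings. Those readings are fewer, but denser night sampling could disturb sleep and is not proposed, so night noise is no part of the avoidable loss. A reader might also infer that waking readings are being counted as night. The documents set no clock window that would cause this and give no count of such readings, so no size can be attached to it.

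It is tempting to say that actigraphy settles sleep and wake for every recording. Item 11 repeats "also the actigraph as done during the screening phase" at 3 months but does not tie it to the BP day. At baseline the protocol outline describes wear until the extended sleep study, while the eligibility procedures only permit wear up to the morning of randomization. Overlap is possible but not assured.

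**Conclusion.** The point holds as a minor one. Hourly sampling through waking hours leaves avoidable noise in daytime and 24-hour BP change. Under the assumed SDs, 30-minute waking readings would cut daytime change variance by about 4 to 14% with independent readings and about 1 to 9% with hourly autocorrelation of 0.3 to 0.5. The 24-hour mean gains at most about 2 to 8%, where the upper end needs 20-minute and independent readings. Nighttime BP gains nothing.

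The direction follows from the protocol's interval alone. The size depends on BP variability that the documents do not give, so confidence in the figures is low. A reader might infer that the BP comparison is biased or that a null BP result would be explained by the interval. Neither is supported: the same schedule applies to both arms at both visits, and most of the variance of change remains even in the least favourable case shown for daytime BP (72% of it).

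**What to change.** **For recordings not yet made.** In section 4, item 4, program readings every 20 to 30 minutes during waking hours and leave the night hourly. The cost is device programming and more daytime cuff inflations for one day at each of two time points. For this trial's completed recordings the change comes too late.

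**For existing recordings.** In section 7c, state how readings are assigned to day and night. Classify each as sleep or wake from the actigraph, or from the sleep-study EEG at baseline, wherever that source overlaps the BP recording. State the rule for recordings without overlap, and use the same source at both visits where possible. Report the number of valid readings per period. This costs SAP wording and analyst time.

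**Analysis.** Keep the planned baseline-adjusted analysis of period means. If individual readings are modelled, include a participant-by-visit random effect; a participant intercept alone would understate the standard error of change.
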